### **5.4 Subject Withdrawal and Replacement**

Subjects may withdraw from the study at any time and for any reason without penalty or prejudice to his or her future medical care. If a subject is prematurely withdrawn from the study for any reason, the reason(s) for withdrawal must be recorded in the Subject’s source documentation and on the eCRF.

The Investigator must make every effort to perform the Early Termination evaluations. This visit shall take place as soon as possible after it is determined that the Subject will be withdrawn from the study and will comprise the observations and procedures scheduled at the next visit.

## **6 CELUTION & PUREGRAFT SYSTEMS**

### **6.1 Celution& Puregraft System Descriptions**

The Celution System consists of a stand-alone re-useable hardware unit called the Celution Device, the Celution Consumable Set, and Celase®. The Celution System prepares an ADRC output from adipose tissue collected by standard liposuction techniques.

Following the collection of tissue, the adipose tissue is introduced into the device's collection canister in order to wash the adipose tissue and remove deleterious substances (such as cellular debris)(Detailed instructions for use are found in the *Celution User Manual, the Celution Consumable IFU and the Celase IFU*).

The Puregraft 50 System is a sterile, single use, closed system intended for the preparation and delivery of autologous fat grafts back to the same patient for cosmetic and reconstructive surgery applications. The dual filtration bag system utilizes its swabable luer activated valves to connect to an off-the-shelf sterile luer lock syringe and its attached slider is used to facilitate the movement of liquids through the filter mesh and out of the Puregraft bag through the drain stub as waste. Detailed instructions for use are found in the Puregraft IFU).

## **6.2 Device Characterization and Intended Use**

In combination with the Puregraft 50 System, the Celution System (Celution Device, Celution Consumables Set, and Celase reagent) is intended to digest adipose tissue in order to further extract, wash and concentrate adipose derived regenerative cells (ADRCs) intended for combination with autologous fat and reimplantation subcutaneously into the scalp for investigational use in the STYLE clinical trial.

The Puregraft 50 System is intended to process and purify adipose tissue to be combined with concentrated stromal stem cells and other associated progenitor cells intended for autologous implantation subcutaneously into the scalp for investigational use in the STYLE clinical trial.

## **6.3 Contraindications**

1. Non-autologous use is contraindicated
2. Use of any tissues other than adipose is contraindicated

## **6.4 Intended Clinical Performance**

The Celution System is designed to process lipoaspirated tissue and separate ADRCs from adipose tissue by enzymatic disassociation of the tissue and using buoyancy differences to separate the ADRCs from lipid containing adipocytes at the point of care. When ADRCs are prepared using the Celution System, the resultant cell suspension contains all of the components naturally occurring in the native tissue. Preparation of autologous ADRCs for subcutaneous delivery using the Celution System involves no cell culture and can be prepared and re-implanted into the same patient within three hours from completion of lipoaspiration.

The total viable cell count and percentage viability for each sample will be used as the acceptance criteria. This will be assessed for each patient to decide whether the cell output is acceptable, and to prepare the prescribed dose. The viable cell count will be performed by the commercially available NucleoCounter® Automated Cell Counting System. Using a small sample of the Celution System output, the NucleoCounter Automated Cell Counting System provides a count of both live and dead nucleated cells in the total sample. All personnel involved will be trained according to standardized procedures and work instructions. Cytori has performed characterizations of the live cell output obtained by the Celution System and this is consistently

70% viability or greater. This sample count is used to calculate the total number of live nucleated cells from the total preparation, to arrive at percentage of viable cells that are available for introduction into the patient.

The Puregraft System is designed to prepare purified lipoaspirate. This purification involves the near complete removal of free lipid, RBCs, and WBCs. All personnel involved will be trained according to standardized procedures and work instructions.

## **6.5 Celution® & Puregraft System Output; Physical, Chemical, and Pharmaceutical Properties of ADRCs**

The output of the Celution System is an ADRC output obtained from autologous lipoaspirate tissue. The suspension of viable ADRCs has been characterized with an average viability of >70% and the average yield is  $3.24 \times 10^5 \pm 1.48$  of mononuclear cells per gram of adipose tissue entered into the Celution System. An index of regenerative cell potential, the CFU-F assay, shows that 1.51% of those ADRCs form colonies (mean range of 0.13 to 4.08% colony forming units).

The product is a suspension of cells in a diluent. The cellular components of the suspension are made up of nucleated and non-nucleated cells. The non-nucleated cells are red blood cells (RBC) that comprise > 95% of the total cell suspension. The nucleated cells make up approximately 0.1 – 5% of the total cell suspension. Nucleated cells are present in the following approximate minimum percentages: CD 31+, CD 34+ (> 2%); CD 34+, CD 31-, CD 45- (> 10%); CD 45+, CD 31-, CD 34- (> 15%). The combination of these three phenotypes will account for greater than 90% of nucleated cells in the product. [Table 1](#) summarizes the ADRC cellular suspension processed by the Celution System.

**Table 1. ADRC cellular suspension components and concentrations**

Cell Type	Phenotype	Relative Identity of Nucleated Cell Population	% of total cell suspension
Non-nucleated Cells	Red Blood Cells		> 95%
Nucleated Cells	CD 31+, CD 34+	> 2%	0.1-5%
	CD 34+, CD 31-, CD 45-	> 10%	
	CD 45+, CD 31-, CD 34-	> 15%	

## **Puregraft 50 System**

The Puregraft 50 System is used in conjunction with a lipoplasty device (user supplied) and does not contact the patient as it does not connect to vacuum. The Puregraft 50 System is only used on the back table in the operating room to rinse and filter an adipose tissue graft and prepare the graft for eventual injection back into the same patient during the same surgical procedure. The Puregraft 50 System is a bag with two tubing stubs/ports (tissue and drain) and is designed to harvest, rinse and filter the adipose tissue, and subsequently drain excess rinse solution away

from the adipose tissue. The rinsed and filtered adipose tissue is then removed from the Puregraft bag using syringes (user supplied) and ultimately transplanted back into the same patient. The Puregraft 50 System includes a slider tool that is attached to the exterior of the Puregraft bag. The slider is used to compress the Puregraft bag as a means to facilitate the movement of liquids through the filter mesh and out of the Puregraft bag through the drain stub/port as waste.

## 6.6 Proposed Mechanism of Action of Cell Enriched Autologous Fat Grafts

The proposed mechanism of action of autologous fat grafts enriched with ADRCs prepared with both the Puregraft and Celution Systems is postulated to be follicular niche stimulation. This stimulation is believed to occur through modulation of inflammation, promotion of angiogenesis and prevention of cell apoptosis. Studies suggest that cell enriched autologous graft therapy changes the inflammatory response and augments the regenerative response. Studies have detected significant amounts of paracrine growth factors, which have been shown to facilitate vascularization, and as well as those associated with anti-inflammatory effects, thereby, ameliorating injury by proinflammatory cytokines. Viability characterization of ADRCs as described above in addition to pre-clinical animal data from Cytori and other published reports support this hypothesis.

## 7 STUDY TREATMENTS

Subjects will be randomized 2:2:2:1 to active treatment (autologous fat enriched with ADRCs), autologous fat alone control, or no-fat control as follows:

Active ( $0.5 \times 10^6$ ADRCs/cm  scalp):	20 Subjects
Active ( $1.0 \times 10^6$ ADRCs/cm  scalp):	20 Subjects
Autologous fat alone control:	20 Subjects
No-fat control (saline)	10 Subjects

The study treatment will be administered as subcutaneous injections of either fat or saline into the subcutaneous fat layer of the scalp (40cm^2 of scalp) of each subject. Each square centimeter of scalp will be injected with 0.1 mL of purified autologous fat or saline followed by separate injection of either low or high dose ADRC injection per cm^2 scalp, or saline (fat alone control and the no-fat control). To account for the variability seen in advanced grades of hair loss (Norwood Grade II and IV), treatment areas will be focused in the mid-scalp and crown (vertex). The leading edge of hair loss will not be treated, including the peri-orbital region as fat grafting in the peri-orbital region has been associated with higher-risk complications.

### 7.1 Product Description – Cell-enriched autologous fat

The active treatment used for the STYLE Trial will be cell-enriched autologous fat obtained from the study subject's own adipose tissue which is prepared using the Puregraft and Celution Systems.

The excipients in the cell suspension are composed of residual Celution System reagents and diluent. Specifically, the residual reagents are collagenase (<0.005 Wünch Units/mL) and thermolysin neutral protease (< 30 caseinase Units/mL). The diluent is Lactated Ringers solution (USP).

Adipose tissue processing is detailed in both the *Puregraft* and *Celution System Users Manuals*. Preparation of the active study treatment is provided in the *Study Reference Manual*.

### **7.1.1 Active Treatment Dose Control**

Autologous adipose purified with the Puregraft System can be readily removed directly with a sterile 1mL syringe to obtain a volume of 0.1mL for injection.

ADRC Cell count and viability will be controlled using the NucleoCounter Automated Cell Counting System (Enfield, CT) at each site using the following acceptance criteria:

- Nominal cell count:  $40 \times 10^6$  ADRCs
- A minimum cell count within 50% of the nominal cell count is required (i.e., a dose as low as  $20 \times 10^6$  ADRCs is acceptable if  $40 \times 10^6$  ADRCs is not available)
- Cell viability:  $\geq 70\%$   
If cell viability is  $<70\%$ , as determined by the NucleoCounter Automated Cell Counting System, the subject will not be treated.
- Negative result in Gram stain testing (see [Section 7.3](#))

## **7.2 Product Description – Control Doses**

The fat alone control dose will be purified autologous tissue prepared by the Puregraft System that is not enriched with ADRCs but with saline. The amount of fat injected will be  $0.1 \text{ mL/cm}^2$  of scalp. The fat alone control dose will also include injection of a saline solution which is mixed with 0.1mL to 0.2 mL of the study Subject's own freshly drawn blood to achieve a dilution that is visually indistinguishable from ADRCs. The saline injection of the fat-alone control must test negative in a Gram stain test of sterility prior to being administered (see [Section 7.3](#)). Preparation of the fat-alone control dose is provided in the *Study Reference Manual*.

The no-fat control dose will be  $0.1 \text{ ml/cm}^2$  of scalp of saline injected (delivered by a blunt tip cannula) followed by a second matching dose of saline solution (via a 25G needle) to  $0.1 \text{ ml/cm}^2$  of scalp.

### **7.2.1 Justification of Control Dose**

To reduce the risk of bias (selection bias, performance bias, detection bias and attrition bias), all patients will undergo pre-specified screening procedures, fat harvest, and injection of active treatment or placebo. The justification and rationale of the placebo dose arm include:

1. In the presence of a concurrent placebo control group, demographics and patient selection is more likely to be balanced allowing for more reliable interpretation of study results.
2. Minimize the potential of the Hawthorne effect creating a positive impression of efficacy that may overstate the actual treatment effect.

### 7.3 Study Treatment Pre-Injection Sterility Testing

[figure not shown]
Following cell processing in the Celution System, sterility testing will be performed as described below and more fully in the *Study Reference Manual*.

A negative Gram stain test result is required prior to injection of ADRCs and/or fat alone control. A negative Gram stain test result is not required prior to injection of saline in the no-fat control arm. If the sample is determined to be positive for bacteria then the cellular administration procedure must be stopped and the subject should not receive any study treatment.

Further testing (BacT Alert Culture and Sensitivity) will be performed in order to test for the presence of any low level microbial contamination that might not be apparent in the gram stain test. Should a culture be deemed positive for microbial activity, the investigator will be immediately notified. The study patient will be evaluated and a course of treatment and/or antibiotics may be administered, as determined by the study investigator. The source of the contamination will be evaluated as appropriate. The FDA and IRB will be notified within 15 days of the investigator being made aware of any positive test results.

The following flow chart describes the activities associated with positive or negative outcomes in these two tests of sample sterility.

**Figure 3: Sterility Testing of ADRC and Fat Alone Control Samples**

#### 7.3.1 ADRC Characterization

In order to characterize the phenotype of ADRCs obtained from patients with alopecia androgenetica, adipose tissue will be obtained during the elective cosmetic liposuction.; up to 360 mL of this tissue (maximum that can be processed by Celution Device) will be used to prepare the active study treatment (ADRCs) using the Celution System. Once it is determined that the cell dose has been achieved according to criteria described in [Section 7.1.1](#), any remaining adipose tissue may be shipped to an outsourced facility of the Sponsor (if within two hours of the outsourced laboratory) according to procedures outlined in the *Study Reference Manual*.

In the Sponsor's outsourced contract laboratory, ADRCs will be prepared from collected adipose tissue using the same Celution System as used in the clinic and the cell output characterized using colony forming unit – fibroblast (CFU-F), a measure of the number of adipose stem cells, and multiparametric flow cytometry analyses used to define the major non-progenitor cell populations in ADRCs. In the flow analyses ADRCs will be stained using antibodies directed to CD31, CD34, CD136 and CD45 proteins. Based on the expression of these four markers, the major populations will be defined as follow:

Leukocytes	CD45+
Endothelial Cells	CD34+/CD31+/CD45-
Stromal Cells	CD34+/CD31-/CD45-
Mural cells	CD34-/CD31-/CD45-/CD146+

If sufficient cells are available, additional characterization of subpopulations will be performed using antibodies such as CD3, CD14, CD19, and CD16/56.

## 8 STUDY ASSESSMENTS

All assessments will be conducted at specific time points as outlined in this section and in the Schedule of Assessments in [Appendix A](#).

### 8.1 Medical History, Physical Examination & Vital Signs

A complete medical history will be collected at the Screening Visit and will include demographic information as well as current and past medical conditions. Updated medical history information is to be collected at the Day -1 including any event that has occurred since the Screening Visit that could be considered an adverse event. Any adverse event that occurs after the ICF is signed and prior to administration of the study drug is to be recorded as an update to the Medical History.

Physical examinations should be based on the following body systems: general appearance, head (ear, eyes, nose and throat), cardiovascular, respiratory, abdomen, musculoskeletal, neurological, lymph nodes, and skin. Vital signs to be obtained include the following:

- Blood pressure (systolic and diastolic; mm/Hg)
- Heart rate (beats per minute)
- Body temperature (°F)
- Respiration rate (per minute)

## **8.2 Hair & Scalp Evaluation Assessments**

The physical status and satisfaction of the subjects' scalp and hair will be evaluated using several assessment tools. The assessment tools are listed below and detailed information and instructions provided in the *Study Reference Manual*.

- Hair Investigator Satisfaction Survey
- Patient Satisfaction Survey
- Trichogram analysis
- Global photography

## **8.3 Prior and Concomitant Medications**

Any medication a subject receives is considered a concomitant medication, and must be recorded in the subject's source documentation throughout the study. All concomitant medications will be recorded in the eCRF from 90 days prior to screening through 24 weeks post procedure.

Information to be recorded on the eCRF will include: generic medication name, route of administration, dosage, indication, start date, and stop date. Medications used as part of the liposuction and injection procedure do not need to be recorded in the eCRF but should be recorded as part of the operative records. As needed analgesic medications will be recorded by the subject's in a daily medication diary for the 14 days immediately preceding the next study visit.

### ***8.3.1 Prohibited Medications***

Subjects should not receive the following medications:

- Minoxidil, or any oral or topical medication including over the counter and herbal medications for the treatment of hair loss within 6 months of study screening, or finasteride or dutasteride within 12 months of study screening
- Treatment with an investigational product or procedure within 30 days of study screening
- Systemic steroids exceeding prednisone 10 mg daily (or equivalent)
- Biologic agents or immunosuppressive medications within 90 days of the Screening Visit

If treatment with any prohibited medication becomes necessary during study participation, the subject will be discontinued from the trial.

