## STYLE TRIAL - PROTOCOL SUMMARY

Title	Subcutaneous Transplantation of Autologous Cell Enriched Adipose Tissue For Follicular Niche Stimulation in Early Stage Alopecia Androgenetica (STYLE): a Randomized, Blinded, Controlled Trial
Test Products	Celution® System (Celution Device, Celution Consumable Set and Celase) used for processing of Autologous Adipose Derived Regenerative Cells (ADRCs) combined with adipose tissue processed and purified with Puregraft® 50 System
Objective	The primary objective of this study is to evaluate the safety and feasibility of the Celution and Puregraft Systems in the processing and preparation of an autologous fat graft enriched with adipose-derived regenerative cells (ADRCs) in the treatment of early alopecia androgenetica.
Design	Prospective, Randomized, Controlled Safety and Feasibility Trial
Sample Size	70 patients (40 ADRC + adipose, 20 fat only control, 10 no-fat control )
Study Location	Up to (8) sites in the United States
Indication	Androgenic Alopecia (Androgenetica Alopecia, AGA)
Visit Schedule	Screening (Day -28 to Day -7), Pre-Procedure Day (Day -1)Procedure Day (Day 1), and follow up visits at weeks 1, 6, 12, 24 and 52 weeks
Treatment Arms	
Subjects will be randomized 2:2:2:1 to receive either 0.1ml/cm^2 scalp of autologous fat enriched with 0.5 x 10^6 ADRC/cm^2 scalp (n=20), 0.1 ml/cm^2 scalp of autologous fat enriched with 1.0 x 10^6 ADRCs/cm^2 scalp (n = 20), 0.1ml/cm^2 scalp of autologous fat enriched with a matching saline control (fat alone control; n=20), or 0.1 ml/cm^2 scalp of saline enriched with a matching dose of saline (no-fat control; n=10). In each subject, 40 square centimeters of scalp will be treated.
 
The study treatment will be delivered in the subcutaneous adipose layer of the scalp in via two separate injections – one of either 0.1ml/cm^2 scalp of adipose or saline followed by a second injection of ADRCs or saline per square centimeter of scalp.

Primary Endpoint	Safety & tolerability through 24 weeks
Secondary Endpoints	
 
• Trichograms (Hair Growth) at 24 weeks
 
• Trichograms (Hair Density) at 24 weeks
 
• Global photographs to assess scalp coverage at 24 weeks
 

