## **4.5 Study Endpoints**

### ***4.5.1 Primary Endpoint***

Safety & tolerability throughout 24 weeks

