### **9.7 Early Termination Evaluation**

Subjects that discontinue early from the study, unless consent is withdrawn, shall have an Early Termination (ET) evaluation. This visit shall take place as soon as possible after it is determined that the Subject will be withdrawn from the study.

If the ET Visit occurs prior to the Week 24 visit the observations and procedures for the ET Visit are the same as those required at the Week 24.

The reason for early withdrawal must always be clearly documented in the Subject's source documentation. Contact with the Subject must be attempted to determine overall health status, and contact details must be documented in the Subject's source documentation. If lost to follow-up, details of three contact attempts must be documented in the Subject source documentation and every effort must be made to determine if the Subject has expired.

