#### 10.1.1 *Subcutaneous Delivery Risk Analysis*

Risks involved with subcutaneous delivered adipose plus cells include:

- Hematoma or bleeding
- Infection
- Inflammation, rash, or papules at the injection site
- Nerve injury, pain, paresthesias or sensory disturbances
- Diminished function
- Shock loss

Direct intramuscular injections of Celase has been carried out in rodent models showing a margin of safety of greater than 10 for injection of Celase into the heart muscle. In addition, intra-ventricular applications of ADRCs into rat hearts during efficacy studies did not result in adverse events over 12 weeks of follow-up. Further, as noted above, 21 patients treated by direct injection into the muscle of the heart in the course of the PRECISE study exhibited no adverse events associated with ADRC injection. In addition, a study of 12 patients with subcutaneous injection in the fingers of patients with scleroderma showed minor adverse events and no serious adverse events.

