## **11.5 Subject Disposition & Analysis Populations**

Reasons for withdrawal post-randomization will be summarized.

The treatment analyses will be performed on intent-to-treat basis as well as on a per-treatment-evaluable basis, as defined below:

Safety: All treated subjects; subjects will be analyzed as treated.

Intent-to-Treat (ITT): All randomized subjects; randomization will occur on procedure day prior to liposuction. Subjects will be included in the analysis as randomized

Per-Treatment-Evaluable (PTE): All randomized subjects who have received treatment and follow-up information is available. Protocol violators, where the violation is judged to affect the interpretation of the treatment effect will be excluded. All exclusions will be made prior to the breaking of the treatment blind.

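### After the single Day 1 procedure, the prohibited-medication rule in Section 8.3.1 stops no treatment but ends scheduled safety and hair follow-up, possibly for reasons related to outcome

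*Combined protocol and SAP*

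**What the plan says.** Section 8.3.1 of Rev B lists four kinds of prohibited medication or treatment and ends: "If treatment with any prohibited medication becomes necessary during study participation, the subject will be discontinued from the trial". Rev A has the same sentence. The discontinuation is from the trial, not from treatment.

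The protocol summary gives the schedule as "Procedure Day (Day 1), and follow up visits at weeks 1, 6, 12, 24 and 52 weeks". Section 9.3 describes one harvest and injection session and no repeat dosing.

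The primary endpoint in Section 4.5.1 is "Safety & tolerability throughout 24 weeks".

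After discontinuation, two provisions remain:

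- Section 9.7 requires one Early Termination visit: "This visit shall take place as soon as possible after it is determined that the Subject will be withdrawn from the study". Before Week 24, its content is that of the Week 24 visit. Section 5.4 instead gives it the content of the next scheduled visit.
- Section 12.2 keeps serious adverse events already experienced under observation until they resolve, stabilise or are explained.

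For analysis, Section 11.5 defines "Intent-to-Treat (ITT): All randomized subjects" and a safety population of all treated subjects. Section 11.6 leaves safety data unimputed. It fills ITT efficacy gaps mainly by last observation carried forward (LOCF), with multiple imputation as a sensitivity analysis, and leaves per-treatment-evaluable (PTE) data unimputed.

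**The concern.** In a trial with continuing treatment, a rule of this kind has something to stop. Here, once the Day 1 injections are done, all that remains is observation.

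The reasons for starting a listed drug may lie in the outcomes under study. Section 10.1.1 names "Inflammation, rash, or papules at the injection site" and shock loss as risks of the injection, and the list includes systemic steroids above a stated level and immunosuppressive agents. It also includes hair-loss drugs, which a subject with a poor result might want. Section 5.3 lists investigators among the unblinded. If they judge necessity, as would be usual although the documents do not say so, the loss could differ by arm.

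Two results are at stake. New adverse events after the early termination visit would not be collected at scheduled visits, inside the window that defines the primary endpoint. The 24-week hair comparisons would use a value taken earlier than Week 24 for these subjects.

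**Working it through.** **Inputs.** Arms of 20, 20, 20 and 10 (Section 5.2); this agrees with the total in Section 11.2, since 70 × 2/7 = 20 and 70 × 1/7 = 10. The primary window is 24 weeks (4.5.1). Section 11.2 says that the sample size rests on no power calculation, so there is no power figure to reproduce. The documents give no rate of prohibited-medication use; 5–20% of an arm is assumed below for illustration.

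**1. What is left after a discontinuation.** Read together, 8.3.1, 5.4, 9.7 and 12.2 leave one visit plus follow-up of existing serious events. No section keeps the subject in the remaining Appendix A visits. The content of that one visit is itself in conflict. Under 9.7 it includes the Week 24 photography and trichogram marked in Appendix A. Under 5.4, a subject discontinued before Week 1 gets Week 1 procedures, which include no hair assessment. LOCF would then have only baseline to carry, and 11.6 does not say whether that is allowed.

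**2. Share of the primary window lost.** Discontinuation at Week 6: (24 − 6)/24 = 75%. At Week 12: (24 − 12)/24 = 50%.

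**3. Precision.** With zero events among n subjects, the exact one-sided 95% upper bound is 1 − 0.05^(1/n).

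| Lost | One arm: n followed | Bound | Both ADRC arms: n followed | Bound |
|---|---|---|---|---|
| 0% | 20 | 13.9% | 40 | 7.2% |
| 5% | 19 | 14.6% | 38 | 7.6% |
| 10% | 18 | 15.3% | 36 | 8.0% |
| 20% | 16 | 17.1% | 32 | 8.9% |

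**4. Informative loss, safety.** Assume that 10% of the 40 ADRC subjects would have a late adverse event (4 expected) and that 10% (4 subjects) are discontinued before it could be seen.

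- Late risk in those 4 of 20%: 0.8 events unseen. Observed rate (4 − 0.8)/40 = 8.0% of all treated, or 3.2/36 = 8.9% of those still followed.
- Late risk of 40%: 1.6 unseen. (4 − 1.6)/40 = 6.0%, or 2.4/36 = 6.7%.
- Late risk of 10%, the same as everyone: 0.4 unseen. (4 − 0.4)/40 = 9.0%, but 3.6/36 = 10.0%.
- Late risk of 0%: none unseen. 4/40 = 10.0%, but 4/36 = 11.1%.

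A crude percentage of all treated subjects cannot rise through unseen events, and it falls whenever any are missed. A rate among those still followed can move either way, depending on the late risk of those lost.

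**5. Informative loss, hair.** As an extreme case, suppose that the worst-responding fraction d of one arm has no Week 24 value and nothing is imputed, as in the PTE analysis. The mean of the rest shifts upward by φ(z_d)/(1 − d) standard deviations, where φ is the standard normal density and z_d its d-quantile. This gives 0.109 for d = 5%, 0.195 for 10% and 0.350 for 20%. In the ITT analysis an early value is carried forward instead, and the direction of error depends on arm and timing.

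**The case against.** The case on the other side has substance.

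- **The trigger may be narrow.** Three of the four list items are timed to screening; the hair-loss item, for example, reads "for the treatment of hair loss within 6 months of study screening, or finasteride or dutasteride within 12 months of study screening". Only the systemic-steroid item has no such window. It is also not obvious that a hair-loss drug taken after a disappointing result has become necessary. A reader might infer that every listed class clearly triggers removal after Day 1; the text does not establish that. This stands, and it is a reason to clarify the rule.
- **The rule does more than end follow-up.** A reader might infer that this is its only effect. Between consent and Day 1, however, it also stops a subject from being treated. This stands; the criticism applies only after the procedure.
- **The direction of bias is not fixed.** A reader might infer that the loss always makes the safety profile look cleaner. Step 4 shows that this depends on the denominator and on the late risk of those lost. The reaction that led to the drug would already be on record and stays in the safety population; only later, new events go unseen.
- **The numbers are modest.** The rate is assumed. Section 4.7 already excludes people with autoimmune disease, on immunosuppressive medication or needing chronic systemic corticosteroids. Section 11.3.1 applies no test to the primary endpoint. Losses counted to Week 52 would look larger but fall outside the primary window.
- **Some handling exists.** There is an early termination visit, LOCF and a multiple-imputation sensitivity analysis. Whether a hair value measured on another hair-active drug should count is a choice of estimand.

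These points limit the size and severity of the problem. None restores follow-up. Imputation covers efficacy only, and adverse events that were not collected cannot be recovered at analysis.

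**Conclusion.** The point holds for use after the procedure. Applied then, Section 8.3.1 withdraws no treatment and ends scheduled observation inside the primary safety window. It may do so for reasons linked to a reaction or to lack of effect. The likely result is some understatement of later adverse events, and early hair values standing in for Week 24.

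The size cannot be derived from the documents. At an assumed 10–20% of an arm of 20, the loss is 2–4 subjects and the change in precision is small. The weight rests on informative loss. That in turn rests on two inferences: that listed drugs would sometimes be started because of outcome, and that those subjects carry a higher later risk. Both are plausible from the drug classes and the listed risks; neither is stated in the documents.

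The trial is unpowered and its primary endpoint is judged clinically, so this is a should-fix point, not a fatal one.

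**What to change.** 1. In Section 8.3.1, leave the consequence of use before the procedure as it is. For use after the procedure, state that it is recorded as a protocol deviation, that the subject stays in follow-up for all Appendix A visits unless consent is withdrawn, and that all adverse event data stay in the safety summaries. PTE exclusion can be decided under Sections 11.5 and 11.7.
2. State which on-study use triggers 8.3.1, since most items are timed to screening. Which medications are listed or permitted is a clinical matter for the sponsor and is not addressed here.
3. Reconcile the early termination content in Sections 5.4 and 9.7.
4. In Section 11.6, or in the separate analysis plan promised in 11.1, pre-specify hair values after such use. Report one analysis with observed values and one with post-use values set to missing; the sponsor chooses which is primary.

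The cost is a few sentences and the already scheduled visits for a few subjects. Section 8.3 already has drug name, indication and dates recorded through Week 24. The downside is that some Week 24 hair values will be measured on another hair-active drug, which is why both analyses should be reported.
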